The questionnaires to assess patients' pharyngeal ventilatory perceptual potential/the quality of spontaneous nasopharyngeal perception during ventilation are administered when patients come to the consultation to request the results of the pharyngeal ventilatory perceptual analysis. The examiners are blinded, unaware of the results. Patients are randomly assigned according to their order of arrival. The first questionnaire consists of 7 items selected to aggravate or facilitate upper airways permeability (supine position, modified state of consciousness with muscle relaxation, tongue posture, cephalic flexion, cephalic extension, mandibular protraction, nostrils aperture). This first questionnaire try to evaluate if all subjects are able to feel aggravating or facilitating factors by on/off answers. The second questionnaire consists of 18 items related to upper airway collapsibility. Each item concerns the aggravating or facilitating factors perceived by the patient or the therapist with clinical maneuvers, factors known to be unfavourable to the permeability of the upper airways (snoring, oral ventilation, tonsils, dento-skeletal class, etc.), as well as two questionnaires used in the sleep laboratory of the André Renard clinic (Epworth Sleepiness Scale and FFF questionnaire).

[figure not shown]
For each of these items, the patient's or practitioner's response will be noted.

Performing the examination:

- Sensory-motor awareness of nasal and pharyngeal breathing (patient in a seated position): explain to the patient what to observe and feel and where (soft palate, tonsils, vibration during snoring, etc.)
- Read the questionnaire to the patient: it must be understood
- Ask the patient to answer each item and record the response.

The examination lasts approximately 20 minutes.

This examination requires patient involvement but carries no risks or side effects.

STATISTICAL ANALYSIS PLAN

(translation of the Statistical analysis report download in SAP section from an independent Biostatistician: [name], MyStat.be)

Software used for analysis: R version 4.4.1(R Core Team (2024). R: A language and environment for statistical computing. R Foundation for Statistical Computing, Vienna, Austria. URL <https://www.R-project.org/>) and Microsoft Excel for manipulating and preparing the data tables. data files used and appended: d1_final.csv, d2_final.csv

1 - d1_final.csv: sensitivity parameters taken from 112 patients

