2 - d2_final.csv: parameters taken from 101 patients (excluding CHR patients considered normal after polysomnography)

Discrete variables for classification into groups :

- STATUS3: 2 categories: healthy patients (= non-CHR control patients and normal CHR patients) and pathological patients (= CHR patients affected to varying degrees)
- STATUS4: 4 categories: control patients (= non CHR), normal patients (= CHR N), mild symptom patients (= CHR SL), moderate symptom patients (= CHR SM) and severe symptom patients (= CHR SS).

A. Descriptive statistics (based on file n°1 - sensitivity)

B. Descriptive statistics (based on file n° 2 - predictive score)

C. Normality tests for intermediate and final scores

- Parameter ST1 (SubTotal1) = aggravating parameters

Shapiro-Wilk normality test

- Parameter ST2 (SubTotal2) = facilitating parameters

Shapiro-Wilk normality test

- Parameter ST1+ST2 (SubTotal1+ SubTotal2) = subjective sensitivity of patients

Shapiro-Wilk normality test

- Parameter ISF (Intermediate Final Score) = subjective sensitivity of patients and practitioner

Shapiro-Wilk normality test

- Parameter TFS (Total Final Score) = subjective sensitivity of patients and practitioner + valuable factors

Shapiro-Wilk normality test

D. Spearman correlation tests between final scores and certain variables

E. Non-parametric tests on patient sensitivity :

Given the non-normal distribution of the various variables other than IFS and TFS, non-parametric tests (based on the median of the data) were applied to analyse the differences between the groups (according to the STATUS3 and STATUS4 classification criteria). To analyse any differences in sensitivity between patient groups, Kruskal-Wallis tests were applied. In this type of analysis, having a p-value greater than 1% and ideally greater than 5% would indicate the absence of differences between groups.

Then, to see if the median of a particular group is different from 0 (= no sensitivity: not feeling the differences in airflow induced by the different tests given by the operator), Wilcoxon tests were performed on each group of data. If the p-value is small (less than 5%, ideally less than 1%), the null hypothesis that the score is identical to 0 is rejected. In this case, it means that the patients in the test group feel the differences in airflow depending on their position. This is the case for all the patient groups tested on ST1, ST2 and ST1+ST2.

[figure not shown]

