F. Parametric tests on the prediction of patients' pathological status (SFI and SFT scores):

For these analyses, as the IFS and TFS scores follow a normal distribution, ANOVAs (analyses of variance) were performed. For discrete variables with more than 2 levels of value (STATUS4), a post-hoc 2-to-2 comparison analysis was performed (Tukey) to see which level of the variable differed from one another. Significant values are highlighted in bold red.

[figure not shown]
G. Determination of cut-off values for IFS and TFS:

[figure not shown]
The Cutoff_final txt file includes the various sensitivity and specificity calculations as well as the Youden index in order to determine the best cut-off value (largest Youden). The ROC curves allow the values in the file to be appreciated graphically.

Upper rhino-oro-pharyngeal airway permeability - Subjective neuro-sensory evaluation

Assessment of oro-pharyngeal sensitivity				
Date :	Name:			age:
Tests	Items			Score 1 0
	Aggravation or facilitation felt = 1 No aggravation or no facilitation felt = 0			
Aggravation maneuver	1	Supine position		
Aggravation maneuver	2	Modified state of consciousness (overall relaxation)		
Aggravation maneuver	3	Cephalic Flexion		
Aggravation or Facilitation maneuver	4	Upper-anterior tongue to lower tongue (= aggravation) or lower tongue to upper-anterior tongue (= facilitation)		
Facilitation maneuver	5	Cephalic Extension		
Facilitation maneuver	6	Mandibular protrusion		
Facilitation maneuver	7	Nostrils aperture		
Total Score				... / 7
Comments :				
www.osteovox.be				

Upper rhino-oro-pharyngeal airway permeability - Subjective neuro-sensory evaluation						
Date :	Name :			age: IMC:		
Tests	Items			Scores		
	0	0,5	1	2		
Aggravation maneuver	1	Supine position: aggravation=1 / no aggravation= 0				
Aggravation maneuver	2	Modified state of consciousness (overall relaxation) aggravation=1 / no aggravation= 0				

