Aggravation maneuver	3	Cephalic flexion: aggravation at the start of flexion ($\leq 6^\circ$)=2 / in the middle of flexion ($7\text{--}>10^\circ$)=1 / at the end of flexion ($\geq 11^\circ$)=0				
Facilitation maneuver	4	Cephalic extension: facilitation from the start of extension ($\leq 6^\circ$)=2 / in the middle of extension ($7\text{--}>10^\circ$)=1 / at the end of extension ($\geq 11^\circ$)=0				
Facilitation maneuver	5	Measurement of range: amplitude between cephalic flexion and extension: reduced ($\leq 12^\circ$)=2 / medium ($13\text{--}>20^\circ$)=1 / large ($\geq 21^\circ$)=0				
Facilitation maneuver	6	Mandibular advancement: Physiological=2 / Tooth butt =1 / Anterior crossing=0.5 / no facilitation= 0				
Therapist observation	7	Therapist palpation of the contraction of the buccal floor on inspiration at rest yes=2 / no=0				
Therapist observation	8	Sound perception of ventilation by the therapist: yes=1 / no=0				
Intermediate Final Score (IFS): low risk of OSA ≤ 7.5 / risk of OSA ≥ 8				... / 13		
Aggravated situation	9	Low lingual posture in supine position : yes=2 / no=0				
Subjective perception of nasal permeability	10	Do you regularly have difficulty breathing through your nose? yes=1 / no= 0				
Subjective perception of snoring	11	Do you snore at night? yes=1 / no=0				
Subjective perception of daytime ventilation patterns	12	During the day, you breathe mainly: through the mouth=1 / mixed nose-mouth=0,5 / through the nose =0				

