subjective perception of nocturnal breathing patterns	13	At night, you breathe mainly: through the mouth=2 / mixed nose-mouth=1 / through the nose =0				
Therapist observation	14	Dento-skeletal class: class I or III = 0 / class II = 1				
Therapist observation: Tonsils: grades 0-1-2 =0 / grades 3-4 =1	15	Quote : 				
Therapist observation: Mallampati: grade 1-2 =0 / grade 3-4 =1	16	Quote : 				
Epworth Sleepiness Scale	17	score: ≤ 8 =0 / $9\text{--}>14$ =1 / ≥ 15 =2				
FFF questionnaire	18	score ≤ 10 =0 / ≥ 11 =1				
Final Total Score (FTS): low risk of OSAS ≤ 10 / high risk of OSAS ≥ 11				... / 26		
Comments :						
www.osteovox.be						

Study process adapted from the CONSORT 2010 flowchart.

STUDY GROUP: The final sample included 41 patients diagnosed with OSAH (mild= 9, moderate=18; severe= 14).

The study sample included 13 women and 28 men, with a mean age of 49.30 years, and a mean body mass index (BMI) of 30.70 kg/m².

CONTROL GROUP: The final sample included 60 patients without OSA based on subjective scales used in sleep medicine in Liège (Epworth, Berlin, Pichot, FFF).

The study sample comprised 20 men and 40 women, with a mean age of 41.76 years and a mean body mass index (BMI) of 22.78 kg/m².

Predictability of OSA with a Subjective Screening Scale

Predictive Value of OSA Based on the Evaluation of the Subjective Feeling of the Air Flow
Through Airways, a Randomized Controlled Study

Herstal, February 3, 2023

Favorable Opinion

Composition of the Ethics Committee:

- - [name] - Vascular Surgeon
- - [name] - External General Practitioner
- - [name] - Palliative Care
- - [name] - Anesthesiologist
- - [name] - Geriatrician
- - Maître [name] - Lawyer at the Liège Bar
- - [name] - Hospital Mediator
- - [name] - Psychologist
- - [name] - Social Worker
- - [name] - Hospital Pharmacist
- - [name] - Nurse in the Intensive Care Unit

Subject:

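### The printed risk bands for the final total score leave the attainable score 10.5 without a class

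*Combined protocol and SAP*

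**What the plan says.** The Protocol section introduces the scored form: "The second questionnaire consists of 18 items related to upper airway collapsibility". The form carries two decision bands.

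- After item 8: "Intermediate Final Score (IFS): low risk of OSA ≤ 7.5 / risk of OSA ≥ 8", with a maximum of 13.
- After item 18: "Final Total Score (FTS): low risk of OSAS ≤ 10 / high risk of OSAS ≥ 11", with a maximum of 26.

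Two items can score half a point. Item 6 (mandibular advancement) ends with "Anterior crossing=0.5 / no facilitation= 0". Item 12 (daytime breathing) is scored "through the mouth=1 / mixed nose-mouth=0,5 / through the nose =0". The visible text gives no rounding rule and no indeterminate zone.

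SAP Section C defines "Parameter TFS (Total Final Score) = subjective sensitivity of patients and practitioner + valuable factors". I read this TFS as the form's FTS; the heading of Section F calls it SFT. Section G says that a file named Cutoff_final "includes the various sensitivity and specificity calculations as well as the Youden index in order to determine the best cut-off value (largest Youden"). It adds: "The ROC curves allow the values in the file to be appreciated graphically". Neither that file nor the figure in Section G is visible. Section G does not name its data set. File 2, the predictive-score file with 101 patients, matches the 41 cases and 60 controls described after the form.

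**The concern.** A screening form has to give every attainable score a result. A half-point scale with bands ending at 10 and starting at 11 omits one value, and that value lies on the decision boundary. The intermediate score on the same form is banded correctly for half points, and nothing in the text suggests that the gap in the total score is deliberate.

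Two things are at stake. A subject who scores 10.5 gets no result. And if any study patient scored 10.5, the printed bands fit two different empirical thresholds, so a reader cannot tell which one the sensitivity and specificity in Cutoff_final describe.

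A secondary question concerns Section G. Its visible text selects the cut-off with the largest Youden index and mentions no confidence interval, resampling or separate validation sample. If accuracy is described on the patients used to choose the cut-off, it is expected to be somewhat optimistic.

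**Working it through.** **1. Reproduce the form's own maxima.** Scores as printed on the second questionnaire:

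- Items 1, 2, 8, 10, 11, 14, 15, 16, 18: {0, 1}
- Items 3, 4, 5, 13, 17: {0, 1, 2}
- Items 7, 9: {0, 2}
- Item 6: {0, 0.5, 1, 2}
- Item 12: {0, 0.5, 1}

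Maximum for items 1 to 8: 1+1+2+2+2+2+2+1 = 13. Items 9 to 18 add 2+1+1+1+2+1+1+1+2+1 = 13, giving 26. Both agree with the form.

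**2. Enumerate the totals.** Items 1 to 8 have 2×2×3×3×3×4×2×2 = 1,728 answer patterns and items 9 to 18 have 3,456, so there are 1,728 × 3,456 = 5,971,968 in all.

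| Score | Attainable values | Values in neither band |
|---|---|---|
| IFS (≤ 7.5 / ≥ 8) | 26 | none |
| FTS (≤ 10 / ≥ 11) | 53 (every half-point from 0 to 26) | 10.5 only |

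The total 10.5 arises from 252,453 patterns, or 4.2% of patterns (not of patients). One example is an IFS of 7.5, plus snoring (1), plus mouth breathing at night (2).

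**3. When a half-point total occurs.** Exactly one of items 6 and 12 must be scored 0.5. With shares p6 and p12 of subjects scoring 0.5 on those items, P(half-point total) = p6(1 − p12) + p12(1 − p6). This is 0.049 at 2.5% each, 0.095 at 5% each and 0.18 at 10% each. If all answers were equally likely it would be (1/4)(2/3) + (1/3)(3/4) = 5/12 = 0.417.

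**4. How many patients might be at 10.5 (illustration only).** The documents give no score distribution. Assume normal scores with control mean 8, common SD σ of 2 to 4.5, true AUC 0.7 to 0.9 and case mean 8 + √2·σ·Φ⁻¹(AUC). With half-point share h and group mean μ, P(10.5) = h[Φ((11 − μ)/σ) − Φ((10 − μ)/σ)].

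For σ = 3.5, AUC 0.8 and h = 0.10, the case mean is 12.17. The probability is 0.0088 per control and 0.0102 per case. The expected count is 60 × 0.0088 + 41 × 0.0102 ≈ 0.95, and the chance of at least one is 0.61.

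| Half-point share | Expected number at 10.5 among 101 | Chance of at least one |
|---|---|---|
| 5% | 0.3 to 0.7 | 0.27 to 0.49 |
| 10% | 0.6 to 1.4 | 0.46 to 0.75 |
| 25% | 1.6 to 3.4 | 0.79 to 0.97 |
| 42% | 2.6 to 5.7 | 0.93 to over 0.99 |

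**5. Effect per patient.** Moving the threshold between ≥ 10.5 and ≥ 11 changes sensitivity by 1/41 = 2.4 points for each case at 10.5, and specificity by 1/60 = 1.7 points for each control at 10.5.

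**6. Optional point, same assumed distributions.** I simulated 41 cases and 60 controls, chose the cut-off with the largest Youden index, and compared apparent with true Youden at that cut-off. With 5% to 50% half-point scores, the mean optimism is 0.04 to 0.08 for FTS. For IFS (control mean 6, SD 1.5 to 2.5) it is 0.03 to 0.08. The sampling SD of Youden is 0.07 to 0.08. At AUC 0.8 the 5th to 95th percentile of the chosen FTS cut-off is about 8.5 to 11 (SD 2), 8.5 to 12.5 (SD 3.5) or 8.5 to 14 (SD 4.5).

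**The case against.** The strongest reply is that no result is shown to change. Section F analyses the scores by ANOVA and does not use the bands. A threshold search in Section G classes every patient at each candidate value, so the gap may lie only in the wording of the form. Bands of ≤ 10 and ≥ 11 are also what an analyst might print if no patient scored 10.5, and the link between the printed bands and Section G is inferred, not stated. All of this stands, and it limits the weight of the point. It does not close the gap: the form still gives 10.5 no class, whatever the source of the bands and whatever the SAP calls the score. Nor is the gap an artefact of text extraction, because the decimals on the form and both half-point items are intact.

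The illustrative counts rest on assumed distributions and range from unlikely to near certain, so they show only that a count is needed.

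Against the optional point, the largest Youden index is a standard way to choose a cut-off, the expected optimism is no larger than the sampling SD of Youden, and the unseen figure or Cutoff_final may already contain intervals. These objections stand, which is why the request is optional and conditional.

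**Conclusion.** The FTS bands are wrong as written and should be fixed. That 10.5 is attainable, unclassed and the only such value among 53 is exact; it depends only on the printed item scores, which reproduce the form's maxima. The consequence for the study's accuracy figures is unknown: nil if nobody scored 10.5, otherwise a matter of which threshold those figures describe. Confidence is high on the gap.

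The lack of internal validation is a possible improvement, held with less confidence. It concerns only the visible text of Section G, its size depends on assumed distributions, and the main point does not rely on it.

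**What to change.** **Needed.**

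- State whether the printed bands come from Cutoff_final.
- Reconcile the FTS bands with the single selected threshold so that they meet at adjacent half-points. Which class 10.5 belongs to is for the sponsor to settle from that threshold; I do not propose one.
- Report how many cases and controls score 10.5.
- Confirm that the reported sensitivity and specificity use the same threshold.
- Use one name for the score, or state that FTS, TFS and SFT are the same.

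The cost is one line on the form, one sentence in the SAP and a count from an existing file.

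**Optional, unless already in Cutoff_final or the figure.**

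- State the file and n used in Section G.
- Repeat the whole cut-off search in bootstrap resamples (for example 2000, stratified 41/60). Report optimism-corrected sensitivity, specificity and Youden with 95% CIs, the bootstrap range of the cut-off, and a 95% CI for AUC.
- Label any data-derived cut-off as not yet validated.
- State whether items, points and category limits were fixed before these data were seen. If they were not, the scoring step must also be repeated in each resample and AUC needs optimism correction too.

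This is a short R script on existing data. Because the SAP text is a translated report of completed analyses, it would be an addendum. Accuracy would look slightly less favourable, and the simple bootstrap removes most but not all of the bias. In a check at SD 3.5, AUC 0.8 and 10% half-points, apparent, corrected and true Youden were 0.490, 0.443 and 0.426, so (0.490 − 0.443)/(0.490 − 0.426) = 73% was removed.

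### Controls were classed as OSA-free on scales that include Epworth and FFF, and both are scored in the FTS, so FTS accuracy can be inflated by an unknown amount

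*Combined protocol and SAP*

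**What the plan says.** - **Controls.** The control group paragraph at the end of the document says: "The final sample included 60 patients without OSA based on subjective scales used in sleep medicine in Liège (Epworth, Berlin, Pichot, FFF". It describes no polysomnography for them.
- **Index score.** The Protocol section puts the "Epworth Sleepiness Scale and FFF questionnaire" in the second questionnaire. They are item 17 (0, 1 or 2 points) and item 18 (0 or 1 point). Both count towards the total, whose printed rule is "Final Total Score (FTS): low risk of OSAS ≤ 10 / high risk of OSAS ≥ 11", out of 26. The IFS covers items 1-8 only, out of 13.
- **Data.** File 2 holds "parameters taken from 101 patients (excluding CHR patients considered normal after polysomnography"). Heading B links this file to the predictive score: "B. Descriptive statistics (based on file n° 2 - predictive score"). Sections F and G do not name a file. STATUS3 nevertheless defines its healthy category as "healthy patients (= non-CHR control patients and normal CHR patients").
- **Analyses.** Section F compares IFS and TFS between status groups by ANOVA. Section G tabulates sensitivity and specificity "as well as the Youden index in order to determine the best cut-off value (largest Youden"), with ROC curves.
- **Status of the SAP.** It is described as a "translation of the Statistical analysis report download in SAP section from an independent Biostatistician", so the analysis has already been done.

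The questionnaire says FTS where the SAP says TFS or SFT. I read these as one score.

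**The concern.** When components of an index test also decide who enters the non-diseased group, the test is partly compared with itself. A candidate control with a high Epworth or FFF score is less likely to be kept as OSA-free, so the retained controls can score low on items 17-18 because of how they were chosen. This widens the FTS gap in F and raises the AUC and specificity in G. Because G picks the cut-off from the same data, the cut-off, and with it the reported sensitivity, can move too.

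An FTS cut-off is printed on the questionnaire as a screening rule, so its accuracy matters. The text claims no gain of FTS over IFS but sets cut-offs for both. Only the FTS has the direct overlap, so any apparent gain over the IFS could come from it.

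**Working it through.** **1. Reproduce the plan's own figures.**
- Cases: 9 + 18 + 14 = 41. Cases plus controls: 41 + 60 = 101, the size of file 2.
- Items 1-8: 1+1+2+2+2+2+2+1 = 13, the printed IFS maximum.
- Items 9-18: 2+1+1+1+2+1+1+1+2+1 = 13. Total 26, the printed FTS maximum.

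**2. Share of the score that overlaps.** Items 17-18 carry 2 + 1 = 3 points. 3/26 = 11.5% of the FTS; 3/13 = 23.1% of the points added to the IFS; 0 of the IFS. Without them the maximum is 23.

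**3. Share of the non-diseased group that is scale-selected.**
- If F and G use file 2 (an inference from heading B and 41 + 60 = 101): 60 of 60.
- If the polysomnography-normal CHR patients were included after all (about 112 - 101 = 11, also inferred): 60/71 = 84.5%.

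The concern stands on either reading.

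**4. Limits for the direct effect of items 17-18, assuming no score distribution.**
- *Who can change class.* The score moves in half points. With the cut-off fixed at 11 or more and 10.5 counted as negative, items 17-18 can add 1, 2 or 3 points, so only controls whose items 1-16 total 8 to 10.5 can cross. The printed rule leaves 10.5 unclassified; if that is its own class, the band is 7.5 to 10.5.
- *Specificity.* Each control that crosses is worth 1/60 = 1.7 percentage points; for illustration, 3/60 = 5 and 6/60 = 10.
- *Sensitivity.* If the re-derived cut-off falls, each extra case captured is worth 1/41 = 2.4 points.
- *AUC.* There are 41 × 60 = 2,460 case-control pairs. Let d be the case FTS minus the control FTS. Raising the control by k (0 to 3) gives d - k, so order or tie can change only if 0 ≤ d ≤ 3. A full reversal is worth 1/2,460 = 0.0004; 100 reversals, 0.041.

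**5. Direction of the direct effect.** Lowering control scores leaves sensitivity at every cut-off unchanged, and specificity rises or stays the same. The AUC and the maximum Youden index therefore cannot fall. The selected cut-off itself can move either way.

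**6. Illustration under assumed inputs, not an estimate for this trial.** Suppose that items 17-18 have no true discriminating value and that controls are kept only if both score 0. Let items 1-16 have SD 3 to 4 and a true case-control difference of 0 to 4 points. Let 25-60% of unselected people score above 0 on item 17 and 20-50% on item 18. In simulation (400,000 per group before selection), selection alone then does the following:

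| Quantity | Change |
|---|---|
| Mean FTS difference | +0.5 to +1.3 points |
| AUC | +0.03 to +0.12 |
| Specificity at FTS below 11 | +4 to +16 percentage points |

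With no true difference at all, the AUC moves from 0.50 to about 0.53-0.62.

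**The case against.** The overlap itself is not in dispute. The case against concerns its weight and the remedy.

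- **No material effect is shown.** This stands. Without thresholds or a combination rule, a control may still score above 0 on items 17-18. The illustration assumes the strongest form of selection.
- **Dropping two items does not remove selection bias.** This stands as a caveat. Selecting on four scales also shifts any correlated item, and self-reported items 10-13 (nasal difficulty, snoring, day and night breathing route) are candidates. As an illustration, assume items 1-16 have SD 3.5 and a true difference of 2, with about 60% of candidates kept. A correlation of 0.2 or 0.4 with the selection scales then moves the AUC of items 1-16 from about 0.66 to 0.69 or 0.73. The limits in step 4 cover only the direct path, and a gain that survives on 23 points is not proof of no bias.
- **The Youden cut-off can rise as well as fall.** True. In simulated trials of 41 v 60 with assumed inputs and all controls set to 0 on both items, the cut-off fell in about 37-45%, stayed put in 39-46% and rose in 12-23%. Average sensitivity rose by 2-4 points.
- **Undetected OSA among controls could lower apparent specificity.** It could, so the net direction is uncertain. An opposing bias of unknown size does not cancel this one.
- **The missing flowchart and figures may hold the thresholds or the file name.** Possible, so the request for them applies only if they are not already stated there.

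None of this removes the overlap or the value of a rerun.

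**Conclusion.** The concern holds. Two of the four scales that define the controls are also scored in the FTS, and the supplied text for F and G describes no handling of this. Confidence is high for the overlap, not for a material effect: the size is unknown and may be zero. Inflation requires that selection lowered the controls' scores on items 17-18, which is plausible but not shown. ST1, ST2 and the IFS have no direct item overlap, although the IFS comparison shares the questionnaire-defined controls. This should be fixed before FTS accuracy, or any advantage over the IFS, is relied on.

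**What to change.** 1. In F and G, report beside the 26-point FTS a sensitivity analysis on items 1-16 (maximum 23) with its own re-derived cut-off. Claim no diagnostic gain of FTS over IFS unless it also holds on the 23-point score, and treat that as a necessary check only.
2. Unless the full document already does so, state the thresholds and combination rule used to class controls on the four scales, and name the data file behind F and G.
3. State that accuracy against questionnaire-defined controls is not an unbiased estimate and that the bias can run in either direction.
4. If 18-item data exist for the polysomnography-normal CHR patients, add an exploratory FTS analysis restricted to polysomnography-tested patients, with confidence intervals.

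**Cost.** Items 1-3 need a rerun on item scores for the 101 patients already in file 2, plus disclosure. The rerun is necessarily post hoc. The 23-point AUC may be lower partly because any genuine signal in items 17-18 is lost, and control status stays unverified.

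Item 4 would be imprecise. By Hanley-McNeil, SE² = [A(1-A) + 40(A/(2-A) - A²) + 10(2A²/(1+A) - A²)] / (41 × 11). For an assumed AUC of 0.70, 0.80 or 0.90 the SE is 0.0817, 0.0655 or 0.0432, so the 95% half-width (1.96 × SE) is 0.16, 0.13 or 0.085. One normal patient is 1/11 = 9.1 specificity points.

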- Altered state of consciousness (first sleep stage)
- Mouth breathing and loss of lingual-palatal and labial-labial contact
- Passive craniocervical flexion

Facilitating parameters:

- Cephalocervical extension
- Mandibular advancement
- Tongue protraction
- Efficient nasal ventilation

These considerations allow us to establish an examination protocol to attempt to answer the following questions:

- Can the subject consciously perceive variations in airflow/or intraluminal pressure in the upper airways caused by the various aggravating and facilitating parameters?
- Can the sensations of ventilatory flow/intraluminal pressure felt by the subject constitute a complementary tool for screening for obstructive sleep disorders?

The goal of the clinical examination is to cause instability of the oropharyngeal mechanics. This instability can cause a modification of the pharyngeal lumen and a modification of the resistance of the VAS to the pressure linked to the ventilatory flow. These will lead to a modification of the inspiratory pressure gradient and stimulate the mechanoreceptors located in the VAS. The responses to a questionnaire by subjects who present sleep disorders exposed to these variations in resistance (aggravating or facilitating) on their subjective feeling allows the establishment of a perception scale which, compared to a control group without sleep disorders, will determine if the sensitivity of the inputs is comparable between the groups and if a tool for screening sensory inputs is possible.

Protocol:

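### Controls are labelled free of OSA by questionnaire only, so the specificity in section G applies to questionnaire-negative people, and its bias as specificity for absence of OSA cannot be calculated from the documents

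*Combined protocol and SAP*

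**What the plan says.** The control group paragraph at the end of the document reads: "The final sample included 60 patients without OSA based on subjective scales used in sleep medicine in Liège (Epworth, Berlin, Pichot, FFF"). The study group paragraph gives 41 patients diagnosed with OSA: 9 mild, 18 moderate and 14 severe.

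The SAP lists two data files. The first holds "sensitivity parameters taken from 112 patients". The second, which heading B ties to the predictive score, holds 101 patients, "excluding CHR patients considered normal after polysomnography". STATUS3 nevertheless defines its healthy category as the non-CHR controls pooled with the normal CHR patients.

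Section F compares the intermediate and total final scores (IFS; TFS in the SAP, FTS on the form) between groups by ANOVA. Section G chooses the cut-offs by the largest Youden index: "The Cutoff_final txt file includes the various sensitivity and specificity calculations as well as the Youden index". The form already prints risk thresholds of 8 or more out of 13 for the IFS and 11 or more out of 26 for the total score. The introduction asks whether the patient's sensations can "constitute a complementary tool for screening for obstructive sleep disorders".

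**The concern.** The two groups were classified by different reference standards. Polysomnography is named for the CHR patients judged normal and is implied, though not stated outright, for the 41 diagnosed. The controls have only questionnaires, which cannot rule out OSA without symptoms.

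A control with OSA whom the questionnaires missed is misclassified in one of two ways. If the new score is above the cut-off, a correct detection is recorded as a false positive, which lowers specificity. If it is below, a missed case is recorded as a true negative, and sensitivity is overstated when such cases score lower than the diagnosed ones.

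The study wants to know whether the scale adds to existing screening. A person flagged by the scale and missed by the questionnaires is exactly the person who would show that, and this design counts that person as an error. The text describes no verification of controls, no caveat at the point of analysis and no sensitivity analysis.

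**Working it through.** **1. Counts.** Cases: 9 + 18 + 14 = 41. Cases plus controls: 41 + 60 = 101, which reproduces the size of the predictive-score file exactly. So 0 of its 60 negatives are shown to be verified. The other file has 112 patients, and 112 − 101 = 11 polysomnography-normal CHR patients if that exclusion is the only difference between the files. If F and G instead used STATUS3 with those 11 included, 60 of 71 negatives (85%) would still be unverified.

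**2. Hidden cases that score like diagnosed cases.** Let u be the share of controls with undetected OSA. The documents give no u, Se or Sp, so all three are assumed.

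- Sp_obs = (1 − u)·Sp + u·(1 − Se)
- J_obs = Se + Sp_obs − 1 = (1 − u)·J
- Observed mean difference = (1 − u) × true difference

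With Se = Sp = 0.80 (true J = 0.60), for example 0.90 × 0.80 + 0.10 × 0.20 = 0.74:

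| u (hidden of 60) | Sp_obs | J_obs | Mean difference kept |
|---|---|---|---|
| 5% (3) | 0.77 | 0.57 | 95% |
| 10% (6) | 0.74 | 0.54 | 90% |
| 20% (12) | 0.68 | 0.48 | 80% |

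Not every hidden case becomes a false positive. Of 6 hidden cases, 6 × 0.80 = 4.8 do, and 1.2 count as true negatives. Because J is multiplied by the same (1 − u) at every cut-off, the Youden-optimal cut-off does not move.

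**3. Hidden cases that score lower.** Assume unit-variance normal scores, controls without OSA at 0 SD, diagnosed cases at +1.5 SD, and u = 20%. True sensitivity is taken over 41 + 12 = 53 cases.

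| Hidden cases score | Cut-off chosen | Correct cut-off | Observed Se / Sp | True Se / Sp at chosen cut-off |
|---|---|---|---|---|
| like diagnosed (+1.5) | 0.75 | 0.75 | 0.773 / 0.664 | 0.773 / 0.773 |
| halfway (+0.75) | 0.80 | 0.69 | 0.758 / 0.735 | 0.695 / 0.788 |
| like controls (0) | 0.75 | 0.75 | 0.773 / 0.773 | 0.650 / 0.773 |

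Halfway: (41 × 0.758 + 12 × 0.480)/53 = 0.695. Like controls: (41 × 0.7734 + 12 × 0.2266)/53 = 0.650. The error thus moves from specificity to sensitivity as hidden cases score lower. Of the three scenarios, only the halfway one shifts the cut-off.

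**4. Overlap with the total score.** Epworth (item 17, up to 2 points) and FFF (item 18, up to 1 point) help to label the controls and also supply 3 of the 26 points. Selecting controls for low values on them pushes total-score specificity up, against the effect in step 2. The IFS (items 1 to 8, maximum 13) contains neither.

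**5. Scale against sampling error.** With Sp = 0.85 and 60 controls, the standard error is √(0.85 × 0.15/60) = 0.046. With Se = 0.80, the shift in step 2 is 0.85 − 0.8175 = 0.0325 at u = 5%, below one standard error. At u = 20% it is 0.85 − 0.72 = 0.13, above 1.96 × 0.046 = 0.090.

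**The case against.** The strongest reply is that the size is wholly assumed. No hidden OSA has been shown among the controls, and at 5% the shift is smaller than sampling error. The control paragraph openly says that the label comes from subjective scales. Section G names neither its file nor its status variable, and its figure and output file are not visible, so treating all 60 controls as its negatives is an inference. All of this stands. It limits the point to an unquantified possible bias and a mislabelled estimand, but does not answer either.

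A reader might go further and infer that the published specificity is too low and the Youden cut-off wrong. The documents do not support that. When hidden cases score like diagnosed ones, the cut-off is unchanged. When they score like healthy controls, specificity is unbiased and sensitivity is the quantity in error. For the total score, the Epworth and FFF overlap works in the opposite direction.

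Nor can one simply correct specificity by Sp = (Sp_obs − u(1 − Se))/(1 − u). With Se 0.80, Sp_obs 0.85 and u 20% it gives (0.85 − 0.04)/0.80 = 1.01, an impossible value. It also rests on hidden cases scoring like diagnosed ones, which is doubtful: 18 + 14 = 32 of the 41 are moderate or severe, and the introduction itself suggests that airway perception differs between mild and severe disease.

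**Conclusion.** The concern holds in a limited form. No negative in the 101-patient file is shown to be polysomnography-verified, and that exclusion removes the only negatives the documents describe as verified. Provided F and G use this file, what G reports is specificity against questionnaire-negative people, and F compares diagnosed OSA with the same group.

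As measures of accuracy for OSA itself, these figures may be biased by an amount that cannot be calculated from the documents. Under the assumptions shown, a 20% hidden share could cost about 0.11 to 0.12 of specificity if hidden cases score like diagnosed ones (0.80 to 0.68, or 0.773 to 0.664). It could instead overstate sensitivity by about 0.12 if they score like controls (0.773 against 0.650). At 5% the specificity effect is small beside sampling error. The net direction for the total score is unknown, and an error in the cut-off is possible but not established. The point affects what the study may claim, and it can be dealt with in the analysis and reporting.

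**What to change.** 1. In F and G, rename the comparator *questionnaire-negative controls, polysomnography not done*. Report specificity against that comparator, state which data file and status variable each analysis uses, and make no claim of specificity for absence of OSA.
2. If IFS and total scores were recorded for the polysomnography-normal CHR patients (about 11), report specificity in them separately with an exact confidence interval. It will be imprecise: even 11 of 11 correct leaves a two-sided 95% lower limit of 0.025^(1/11) = 0.715. They are also referred patients, who may be harder to separate from cases.
3. Optionally, add a table for assumed hidden shares of 0, 5, 10 and 20%, with hidden cases scoring like diagnosed cases, halfway, and like controls. Give both sensitivity and specificity. Mark any combination that implies a specificity above 1 as incompatible with the data. Examine movement of the cut-off only where hidden cases score lower than diagnosed ones, since otherwise the answer is always no change.

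The cost is SAP wording, one subgroup estimate and at most one table, with no new patients or sleep studies. The price is a specificity with a narrower meaning, given as a range if the table is added.
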